### 6.4. Long-Term Surveillance Case Analyses

The following analyses will be performed for long-term user who are treated with Xeljanz® for at least 52 weeks.

1) Safety analyses for long-term user

Safety analyses for long-term user will be performed based on data of long-term safety analysis set.

Repeated [6.2. Safety Analyses] - 1) ~ 4).

2) Efficacy analyses for long-term user

Efficacy analyses for long-term user will be performed based on data of long-term efficacy analysis set and analysis at week 52 ( $\pm 15$  days) will be added.

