5. RATIONALE AND BACKGROUND

Xeljanz® (tofacitinib) is a potent, oral janus kinase inhibitor. Xeljanz was initially approved by the Ministry of Food and Drug Safety (MFDS) on 02 April 2014 for the treatment of adult patients with moderately to severely active rheumatoid arthritis (RA) who have had an inadequate response or intolerance to methotrexate. On 20 September 2019, new indications for the treatment of adult patients with moderately to severely active ulcerative colitis (UC) and psoriatic arthritis (PsA).

In clinical trials conducted on patients with moderately to severely active ulcerative colitis, the Xeljanz® (tofacitinib) demonstrated its efficacy and safety in adult patients who have had an inadequate response or intolerance to the basic treatments or biological agents. Ulcerative colitis has the chronic nature of relapse and improvement, most patients experience a number of acute deterioration throughout their life, and in the course of treatment with various drugs, they become resistant to or lose response to the treatment. Currently, there are very limited treatment options available to patients with moderately to severely active ulcerative colitis in terms of efficacy, safety, convenience of administration and quality of life (QoL). Therefore, for patients with limited options who do not respond to current available drugs, there are still many unmet needs for effective and rapid medications with new mechanisms of action.

CCI

Patients who are treated with Xeljanz for at least 52 weeks will be classified as long-term users. Out of all the enrolled patients, at least 18 cases (20%) of long-term users will be followed up to see the long term safety and effectiveness of Xeljanz. This non-interventional post-marketing surveillance (PMS) study is a commitment to MFDS.

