7.3.1.1. Adverse events

Please refer to [Section 9](#) for the definition of non-serious and serious adverse events (SAEs).

Any AEs observed and reported within the reporting period will be recorded on the CRF by the investigator, regardless of the causal relationship with Xeljanz (see [Section 9.2](#)). The AEs can be reported by the patients. The investigator will also collect AE data by asking the patient questions such as “Have you had any health problem since the last visit?”

Check either “yes” or “no” in the AE section of CRF. If “yes”, record the following information:

Event name: Record the name of the AE according to the MedDRA(Medical Dictionary for Regulatory Activities). If there is no appropriate term in the MedDRA, record the name of the AE according to the Medical Terminology Dictionary written by the Korean Medical Society. If possible, specify diagnosis, not individual symptoms.

Date of onset: Record the onset date of the AE. Record approximate date if an actual date is unknown.

Date of recovery: Record the stop date of the AE if the outcome of the AE is recovered or recovered with sequelae (see below). Record approximate date if an actual date is unknown.

Seriousness: Check either “yes” or “no” to indicate if the event is a SAE. If “yes” record appropriate category of the seriousness (see [Section 9](#)for the definition and reporting of SAEs).

Severity: Evaluation of AE severity must be done according to the following categories:

- **Mild**: Not causing any significant problem to the patient. Administration of medicinal product continues without dose adjustment.
- **Moderate**: Causes a problem that does not interfere significantly with usual activities or the clinical status. Dose of the medicinal product is adjusted or other therapy is added due to the AE.

- Severe: Causes a problem that interferes significantly with usual activities or the clinical status. The medicinal product is stopped due to the AE.

If the severity of an AE changes, the AE must be entered separately. Record the stop date of the previous severity and onset date of the new severity – along with completion of all other related items.

Causality assessment: The causal relationship of AEs to the medicinal product must be allocated by the investigator according to the following criteria in alignment with the requirements of MFDS:

- Certain
 - It follows a reasonable time sequence from administration of the drug (before and after the study medication);

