#### 3.4.1. Long-Term Safety Analysis Set

Subjects belonging to the safety analysis set and who are treated with Xeljanz® for at least 52 weeks will be classified as long-term safety analysis set.

The cases below shall be excluded from the long-term safety analysis set in the following order:

- 1) Subjects who are excluded from the safety analysis set
- 2) Subjects who have been administrated Xeljanz® for less than 52 weeks (364 days)

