## **4. Study Endpoints**

### 4.1. Safety Endpoints

Safety will be assessed by the investigator based on all AEs that occur during the 24 weeks (52 weeks for the long-term users) from the first treatment for all patients who have received at least 1 dose of Xeljanz® according to the local product document.

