## 6.2. Safety Analyses

Safety analyses will be performed based on data of safety analysis set. All adverse events in CRF will be classified by SOC and PT according to the latest version of MedDRA.

- 1) All adverse events investigated after administration of Xeljanz® during the study will be summarized with the number of subjects having adverse events, incidence of adverse events with 95% confidence interval (C.I) and the number of adverse events by categorizing as follows:
  - Serious adverse events and serious adverse drug reactions
  - Unexpected serious adverse events and unexpected serious adverse drug reactions
  - Unexpected adverse events and unexpected adverse drug reactions
  - Adverse events and adverse drug reactions
  - Adverse events of safety concerns\*

\*Adverse event with important identified risks and important potential risks in relation to the safety specification under the risk management plan

- 2) All adverse events investigated after administration of Xeljanz® during the study will be summarized with the frequency and percentage of adverse events by categorizing as follows:
  - Occurrence status of adverse events by their severity
    - Mild
    - Moderate
    - Severe
  - Occurrence status of adverse events by their outcome
    - Recovered
    - Recovered with sequelae
    - Recovering
    - Not recovered
    - Unknown

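### The planned long-term safety tables count all AEs from first dose with no split by onset, so they cannot show whether AE risk continues or emerges after week 24

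*SAP*

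**What the plan says.** Protocol section 5 gives the purpose of the longer follow-up: "at least 18 cases (20%) of long-term users will be followed up to see the long term safety and effectiveness of Xeljanz".

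The SAP turns this into output as follows.

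- **Who is in the set.** SAP 3.4.1 takes "Subjects belonging to the safety analysis set and who are treated with Xeljanz® for at least 52 weeks" and excludes anyone with less than 364 days of treatment.
- **What is tabulated.** SAP 6.4 item 1 states "Safety analyses for long-term user will be performed based on data of long-term safety analysis set", and then only "Repeated [6.2. Safety Analyses] - 1) ~ 4".
- **Which events count.** SAP 6.2 item 1 reads "All adverse events investigated after administration of Xeljanz® during the study will be summarized with the number of subjects having adverse events". SAP 4.1 sets the window as "all AEs that occur during the 24 weeks (52 weeks for the long-term users) from the first treatment", and protocol 7.3.1 agrees.
- **What is collected.** Protocol 7.3.1.1 has the entry "Date of onset: Record the onset date of the AE".

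For efficacy, SAP 6.4 item 2 adds a separate week-52 analysis beside weeks 8, 16 and 24. Safety has no counterpart.

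**The concern.** The reason to follow patients for a year is to learn what happens beyond the standard 24 weeks. The planned statistic is the proportion of long-term users with at least one AE at any time from first dose to week 52. A patient with an AE in week 3 and a patient with a first AE in week 45 contribute identically. The count of events is pooled over time in the same way.

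A late rise in AEs can therefore be diluted by early events, and a quiet later period can still sit behind a high long-term incidence. This matters because safety is the primary endpoint, and protocol 9.4.2 names serious infection, tuberculosis, cancer and lymphoproliferative disorders as events of special interest to be monitored, analysed and reported.

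**Working it through.** The documents give no AE rate, power or incidence for this analysis, so there is no plan figure to reproduce. The check has three parts.

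**1. Does any planned table use onset time?** SAP 6.2 items 1-4 cover event category, severity, outcome, seriousness, action taken, causality, incidence by baseline characteristic, and logistic regression. None uses onset date. The visible text has no time-to-onset summary, person-time rate or onset-period table.

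The later part cannot be recovered by subtracting the main table either. That table covers a larger set, and no 0-24 week table is planned for the long-term set alone.

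**2. How much can the pooled figure conceal?** All rates and counts here are assumptions.

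*Share of events.* With a late-to-early event rate ratio r, the share of 52-week events with onset in the first 24 weeks is 24 / (24 + 28r):

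- r = 1: 24/52 = 46%
- r = 0.5: 24/38 = 63%
- r = 0.25: 24/31 = 77%

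*Share of subjects.* Each patient is counted once, at the first AE, with Clopper-Pearson 95% intervals. Two sizes are used for the long-term set: 120, which is 20% of the 600 in SAP 2.4, and 18, the minimum in protocol section 5. Under constant hazard, the expected number of first AEs by week 24 is n × [1 − (1 − p)^(24/52)], where p is the 52-week incidence. For n = 120 and p = 0.40 this is 120 × 0.210, or about 25.

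| Set | Planned figure | Timing of first AEs | First AE after week 24 |
|---|---|---|---|
| n = 120 | 48/120 = 40.0% (31.2 to 49.3) | 48 early, 0 late | 0% (0 to 3.0) |
| | same | 25 early, 23 late (constant hazard) | 19.2% (12.6 to 27.4) |
| | same | 0 early, 48 late | 40.0% (31.2 to 49.3) |
| n = 18 | 7/18 = 38.9% (17.3 to 64.3) | 7 early, 0 late | 0% (0 to 18.5) |
| | same | 4 early, 3 late (constant hazard) | 16.7% (3.6 to 41.4) |
| | same | 0 early, 7 late | 38.9% (17.3 to 64.3) |

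The planned figure is the same in all three rows for each set.

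**3. Would a plain two-column split be enough?** No, for two reasons.

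- *Unequal periods and risk sets.* The periods last 168 and 364 − 168 = 196 days. In the constant-hazard row for n = 120, the raw proportions are 25/120 = 20.8% and 23/120 = 19.2%, which looks like a slight fall. Among the 95 patients still AE-free at week 24, the later risk is 23/95 = 24.2%, which looks like a rise. The weekly hazards are −ln(95/120)/24 = 0.0097 and −ln(72/95)/28 = 0.0099, which are the same apart from rounding to whole patients. Only a measure with the right denominator and time base gives the right answer.
- *Selection.* A patient who stops on day 200 because of an AE has less than 364 days of treatment and is not in the long-term set. The later period of that set therefore omits every AE that ended treatment between day 169 and day 363.

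**The case against.** The strongest defence is that the plan is coherent. The protocol and SAP both define the safety window for long-term users as 52 weeks from first treatment, nothing defines long-term safety as events after week 24, and the study is mainly descriptive. Cumulative 52-week incidence in 52-week users is a proper descriptive measure. This stands: the planned tables are not an error and should be kept. They leave a natural question unanswered.

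A reader might infer that the main tables hold only first-24-week events, so that weeks 24-52 are the only new information in the long-term tables. The documents do not support that. SAP 4.1 counts "based on all AEs that occur during the 24 weeks (52 weeks for the long-term users) from the first treatment", SAP 6.2 counts all AEs during the study, and the long-term set is a subset of the safety set. The later events of long-term users are therefore in the main tables as well. The long-term table is a subgroup table of events already counted, with no onset information added.

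Three further objections have some force.

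- The dummy tables in SAP Attachment 1 are not shown, so a split there cannot be ruled out. The visible text calls for none.
- The limit applies to the planned tables and not to the data, since onset dates are recorded.
- With as few as 18 long-term users, period-specific cells for serious or unexpected events will often be nearly empty. That limits what the addition can show, but the pooled table does not answer the question any better.

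**Conclusion.** The point holds as a cheap improvement. As written, SAP 6.4 item 1 cannot show whether AE risk continues or emerges after week 24. In the illustration with 120 long-term users, a printed 40.0% is compatible with anything from 0% to 40% having their first AE after week 24. If the event rate were constant, 46% of the events in the long-term table would come from the first 24 weeks.

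The finding itself rests on the SAP text. The sizes rest on assumed AE rates and set sizes, and on the undisplayed dummy tables containing no onset split.

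A reader might also conclude that long-term safety should be judged from the second onset period of the long-term set. The documents argue against that, because the 364-day requirement removes late AEs that ended treatment, and such a column could reassure falsely.

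**What to change.** Keep the planned 52-week cumulative tables. Add the following to SAP 6.4 item 1.

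- Present the 6.2 item 1 categories by onset period, day 1-168 and day 169 to week 52. Give subjects, incidence with 95% CI, number of events, and events per person-time, because the periods differ in length.
- Give the later period for the long-term set and also for all safety-set patients still on treatment after day 168, with at-risk denominators.
- State how AEs after week 24 are counted for patients who stop between day 169 and day 363. They do not reach 52 weeks, so a strict reading of SAP 4.1 could limit their window to 24 weeks.
- State that the long-term set excludes AEs that ended treatment before day 364, and do not base the long-term safety statement on that set's second period alone.

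The cost is SAP wording and an extra block of tables from dates already on the CRF. The downsides are small counts and wide intervals in each period, given a protocol minimum of 18 long-term users, and possibly incomplete follow-up after week 24 in patients who stop before week 52. The report should state both.

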## ***Statistical Analysis Plan for rPMS***

Repeated [6.3. Efficacy Analyses] - 1) ~ 7).

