### 2.4. Sample Size Considerations

Sample size calculations are not applicable for this study. At least 600 patients will be enrolled in this study to meet MFDS requirements.

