## **Statistical Analysis Plan for rPMS**

- 4) Analysis of factors that affect the safety
  - In the re-examination report, logistic regression of multivariate analysis will be performed and an odds ratio with 95% C.I and p-value will be presented to identify the factors that affect incidence of adverse events in demographic and other baseline characteristics.
- 5) Analysis for special patient populations [geriatric subjects (aged  $\geq$  65 years), subjects with renal impairment, subjects with hepatic impairment]
  - Adverse events and adverse drug reactions collected in each special patient population will be presented the number of subjects having adverse events, incidence of adverse events and the number of adverse events for each SOC and PT.
- 6) Analysis for population excluded from safety analysis
  - All adverse events investigated after administration of Xeljanz® for population excluded from safety analysis will be summarized with the number of subjects having adverse events, incidence of adverse events with 95% C.I and the number of adverse events by categorizing as follows.
    - Serious adverse events and serious adverse drug reactions (in the re-examination report only)
    - Unexpected serious adverse events and unexpected serious adverse drug reactions (in the re-examination report only)
    - Unexpected adverse events and unexpected adverse drug reactions (in the re-examination report only)
    - Adverse events and adverse drug reactions

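### SAP 6.4 repeats the multivariable logistic regressions in the long-term sets with no sparse-data rule, although the protocol allows as few as 18 long-term users

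*SAP*

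**What the plan says.** SAP 6.4 defines the long-term analyses by reference. For safety it says "Repeated [6.2. Safety Analyses] - 1) ~ 4", and for efficacy "Repeated [6.3. Efficacy Analyses] - 1) ~ 7". Safety item 4 (SAP 6.2) and efficacy item 7 (SAP 6.3) each state that "logistic regression of multivariate analysis will be performed", giving odds ratios with 95% intervals and p-values for the re-examination report. The stated purpose of the safety model is "to identify the factors that affect incidence of adverse events in demographic and other baseline characteristics"; the efficacy model has the same aim for the effective rate.

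The only size given for this subset is in protocol section 5: "Out of all the enrolled patients, at least 18 cases (20%) of long-term users will be followed up". SAP 2.4 says "Sample size calculations are not applicable for this study" and then "At least 600 patients will be enrolled in this study to meet MFDS requirements".

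SAP 3.4.2 makes the long-term efficacy set a subset of the long-term safety set. It requires efficacy data at 52 weeks (±15 days) and drops patients with no general assessment or one rated not assessable. SAP 5.2.1 applies no imputation beyond the date rules.

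**The concern.** The SAP does plan for sparse data in its univariate comparisons: safety item 3 and efficacy item 6 switch from chi-square to Fisher's exact test when expected counts are small. The regressions, which are more fragile, have no such rule. They have no covariate list, selection rule, minimum outcome count, or penalised or exact alternative.

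SAP 6.1 describes at least 12 candidate characteristics: sex, age, disease duration, severity, latent tuberculosis, zoster vaccination, smoking, previous treatment, other diseases, renal impairment, hepatic impairment and concomitant medication. Some need more than one term; smoking alone has four recorded categories in protocol 7.2.5.2.

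With few patients and many terms, some combination of covariates can split the two outcome classes perfectly or almost so (complete or quasi-complete separation). The maximum-likelihood estimate is then infinite, and the software prints very large odds ratios with meaningless intervals. Such output would reach the regulator labelled as factors that affect long-term safety or effectiveness.

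**Working it through.** **Sizes implied by the documents.** The 18 is a floor with no formula behind it, so there is no calculation to reproduce.
- Enrolment implied by the protocol: 18 / 0.20 = 90.
- Long-term users implied by the SAP at the same share: 0.20 × 600 = 120.

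The protocol's study-size section is not in the public text, so the visible documents cannot show which total governs.

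**Outcome counts at the floor.** The smaller class has an expected 18 × 0.4 = 7.2 or 18 × 0.2 = 3.6 patients. With 8 terms that is 7.2 / 8 = 0.9 or 3.6 / 8 = 0.45 patients per term.

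**Test for estimability.** For outcome y (0 or 1) and covariate vector x including the intercept, maximise Σ(2yᵢ − 1)xᵢ′β subject to (2yᵢ − 1)xᵢ′β ≥ 0 for every patient, with β bounded. A positive maximum means separation, so no finite estimate exists. Covariates are simulated as unrelated to outcome. The documents give no outcome rates, prevalences or number of terms, so all three are assumptions.

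**Set A: every covariate at 30% prevalence, 400 data sets per cell; share with separation**

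| Patients | Terms | Minority outcome 40% | Minority outcome 20% |
|---|---|---|---|
| 18 | 5 | 57.5% | 85.3% |
| 18 | 8 | 83.3% | 95.5% |
| 18 | 10 | 96.0% | 99.5% |
| 30 | 10 | 36.5% | 83.3% |
| 120 | up to 10 | 0.0% | 1.3% or less |

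Separate runs of the 30-patient cell differed, so I carry it as roughly 25% to 83%.

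**Set B: prevalences mixed from 5% to 80%, 600 data sets per cell; share with no finite estimate (separation, one-class outcome or rank deficiency)**

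| Patients | Terms | Outcome rate 0.5 | 0.7 | 0.9 |
|---|---|---|---|---|
| 18 | 3 | 13% | 28% | 86% |
| 18 | 5 | 48% | 65% | 96% |
| 18 | 8 | 77% | 90% | 99% |
| 18 | 12 | 100% | 100% | 100% |
| 120 | 8 | 0% | 0.2% | 13% |
| 120 | 12 | 17% | 36% | 90% |

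With every covariate at 50% prevalence, the case most favourable to fitting, 18 patients give failure rates of 29% / 48% / 91% with 5 terms and 68% / 83% / 99% with 8. At an outcome rate of 0.9, all 18 patients fall in one class with probability 0.9¹⁸ = 0.15.

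**Precision when a small model does fit.** The ratio of upper to lower 95% limit of an odds ratio is exp(2 × 1.96 × SE). With 18 patients, 3 to 5 terms and an outcome rate of 0.5 or 0.7, its median is about 97 to 317. That corresponds to a standard error of the log odds ratio of ln(97) / 3.92 = 1.17 to ln(317) / 3.92 = 1.47.

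**The case against.** The strongest reply is that 18 is a minimum. The SAP that orders these regressions also plans at least 600 patients, and at 120 long-term users separation is rare on the set A inputs. That stands, and it makes the point conditional. It does not remove it: 18 is the only long-term number the protocol commits to, and even at 120 a 12-term model or a 90/10 outcome can fail often (set B).

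A second reply is that the SAP never says all baseline variables enter one model. That also stands. With 3 terms and outcome rates of 0.5 to 0.7, failure is only 12% to 31% across the prevalence assumptions. If 12 candidates were first screened at p < 0.05, none would be retained in 82% to 95% of data sets and two or more in at most 2.4%, so the usual result would be no model. But the SAP specifies neither a small model nor a screening step.

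A third reply is that SAP 5.1 requires changed methods to be described in the final report. That gives disclosure after the fact, not a pre-specified fallback.

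A reader might also infer that nearly all long-term users will share one outcome class, because they stayed on treatment for a year. This is plausible for the category Improved, which includes an adequate maintenance effect, but the documents give no rate. Nothing in them supports it for the occurrence of any adverse event over 52 weeks.

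**Conclusion.** The gap in the SAP is real, and its consequence depends on the size reached. At 18 patients, on the set A inputs, no finite estimate exists in about 60% to 85% of data sets with 5 terms and about 85% to 99% with 8 to 10. At 30 patients with 10 terms the share is roughly 25% to 83%, and at 120 about 1% or less. It is higher with rarer covariates, more terms or a 90/10 outcome. At 18 patients the 5-term figure falls to 29% with balanced covariates and a balanced outcome. All these figures rest on assumed model size, prevalence and outcome rate. The finding that many-term models usually fail at 18 holds across every set of assumptions tried.

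Three stronger readings are not supported. The documents do not show that the long-term models will fail whatever size is reached. They do not show that every printed odds ratio would be an artefact: separated fits are, while finite fits near the floor are merely too imprecise to use. And the absence of a covariate list is not peculiar to the long-term sets, since it applies to the main regressions too.

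The 90 and 600 implied by the two documents do not agree. The protocol log records a change of study size in March 2022, after SAP version 1.0 (August 2021), and the SAP log for version 1.1 records only a date rule. An outdated figure in the SAP is thus possible, but this is an inference. The analyses concerned are supportive.

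**What to change.** In SAP 6.4, repeat 6.2 items 1 to 3 and 6.3 items 1 to 6 as standard in the long-term sets. Add a rule for 6.2 item 4 and 6.3 item 7:

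- Fit the regression only if the smaller outcome class reaches a stated minimum relative to the number of model terms, with the terms named in advance.
- Otherwise report descriptive rates with exact 95% intervals, or a Firth-penalised model with one or two pre-named covariates, labelled exploratory.

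The minimum should be chosen and justified before long-term outcomes are examined. Ten patients per parameter is a rule of thumb that nothing in the documents supports. At 120 patients with a 20% minority it would give 120 × 0.2 = 24 and 24 / 10 = 2.4, so about two parameters, and would block models that are estimable there.

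Separately, reconcile the protocol's 18 (20%) with the SAP's 600 and state the expected size of the long-term set.

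The cost is a sentence or two in SAP 6.4, a corrected figure in whichever document is out of date, and possibly fewer model outputs in the long-term section. If the long-term set turns out large, the rule removes little, provided the minimum is set with that case in mind.
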